### **10.8 Cycle Cancellations due to an Adverse Event, including Immune-related Adverse Events, or due to Technical Malfunctions of the Administration Pen**

Adverse events leading to cycle cancellation will be listed.

### **10.9 Multi-fetal Gestation, Biochemical Pregnancy, Spontaneous Abortion, Ectopic Pregnancy and Vanishing Twins**

The incidence of biochemical pregnancy, spontaneous abortion, ectopic pregnancy and vanishing twins will be reported as part of the adverse events summaries described in Section 10.2.2 .

Early pregnancy loss is defined as pregnancy loss occurring before ongoing pregnancy ( $\beta$ hCG to ongoing pregnancy). The incidence of early pregnancy loss will be tabulated. The denominator will be the subjects at risk for early pregnancy loss, i.e. number of subjects with a positive  $\beta$ hCG. Early pregnancy losses will also be grouped as: '  $\beta$ hCG to vital pregnancy' and 'vital pregnancy to ongoing pregnancy'. Summaries will be made overall, by vital pregnancy type and by ongoing pregnancy type. The pregnancy types are defined as 'singleton', 'twin', 'triplets' and 'higher-order multiples' based on number of intrauterine viable fetus(es) at the respective assessment.

## **10.10 Pen Malfunction**

Number of subjects reporting technical malfunctions of the administration pen and the type of malfunction will be tabulated.

## **10.11 Additional Safety Evaluations**

### **10.11.1 Physical Examinations**

Physical examination at end-of-trial compared to baseline (screening) will be summarised in shift tables. Subjects with any abnormal finding will be listed. The list will include both baseline and end-of-trial assessment for comparison.

### **10.11.2 Gynaecological Examination**

Gynaecological examination at end-of-trial compared to baseline (screening) will be summarised in shift tables. Subjects with any abnormal finding will be listed. The list will include both baseline and end-of-trial assessment for comparison.

### **10.11.3 Changes in Body Weight**

Body weight will be measured at screening, on stimulation day 1 (baseline) and at end-of-trial. The actual measurements and the change from baseline will be tabulated.

### **10.11.4 Vital Signs**

Vital signs and their change from stimulation day 1 (baseline) to end-of-trial will be summarised. Shift tables will be prepared to compare the baseline values with the end-of-trial values using the categorisation of low, normal and high reference values. Low, normal and high reference values is specified in the Appendix 1.

For systolic and diastolic blood pressure, a summary table will be prepared displaying the proportion of subjects with a markedly abnormal value at end-of-trial. A break-down of the classification at baseline will be included. The markedly abnormal criteria is specified in Appendix 1. Vital signs will be listed and values categorised as low, high or markedly abnormal will be flagged.

## **10.12 Pregnancy Follow-up**

Pregnancy follow-up information will be collected for all subjects with ongoing pregnancy. All intrauterine viable fetuses at the ongoing pregnancy visits will be accounted for. Neonatal health data will be collected at birth and at 4 weeks after birth for all children born.

All data captured during the pregnancy follow-up will be listed.

### **Live Birth**

Live birth is defined as the birth of at least one live baby. For all live births the type of pregnancy (singleton, twin, triplets and higher-order multiples) will be summarised. Subjects with no information on a live birth will be regarded as not having live birth.

The live birth rate is considered supportive to the primary endpoint and will therefore be analysed in a similar manner as the primary endpoint. Treatment comparisons will be produced for the overall Pan-Asian trial population and for the Chinese population. Summary tables will be prepared by treatment group and age stratum for both the FAS and PP analysis sets. Separate tables will be produced by country. In addition, live birth will be summarised based on the subgroups defined in Section 6.5.

### **Live Rate at 4 Weeks after Birth**

The live rate is defined as all subjects with a live neonate at 4 weeks after birth. The live rate at 4 weeks after birth will be analysed in a similar manner as the primary endpoint. Treatment comparisons will be produced for the overall Pan-Asian trial population and for the Chinese population. Summary tables will be prepared by treatment group and age stratum for both the FAS and PP analysis sets. Separate tables will be produced by country.

### **Late Pregnancy Loss**

A late pregnancy loss is defined as an ongoing pregnancy not followed by live birth. The incidence of late pregnancy losses will be tabulated by treatment group and age stratum for the safety analysis set. Separate tables will be produced by country. The denominator will be the subjects at risk of a late pregnancy loss, i.e. number of subjects with an ongoing pregnancy.

The reason for no live birth (still birth, miscarriage, elective termination) will be tabulated at the fetus/neonate level. In case of elective termination the reason (social circumstances, fetal anomaly, other) will be included. Further, the table will summarise if an autopsy was taken (yes/no). In case the reason for elective termination is 'other' the listing will include the specification as reported by the investigator in the eCRF.

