## 6.10 Post-trial Activities

### Pregnancy Follow-up

All subjects with an ongoing pregnancy will be followed till delivery to gather information on live birth rate. Furthermore, data will be gathered on neonatal health, including any congenital anomalies, at birth and at 4 weeks after birth as described in section 7.4.1.

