### **8.3.6 Pregnancy Losses**

The following terminology should be used for reporting of pregnancy losses during the trial:

Biochemical pregnancy:	Positive $\beta$ hCG test but no gestational sac is observed on later transvaginal ultrasound, or menstruation is reported
Spontaneous abortion:	Positive $\beta$ hCG test but all intrauterine gestational sacs are without fetal heart beat as documented by ultrasound, or there are no viable fetuses observed by ultrasound
Vanishing twin:	Spontaneous disappearance of an intrauterine gestational sac with or without heart beat in a pregnancy where one viable fetus remains as documented by ultrasound
Ectopic pregnancy:	Extrauterine gestational sac with or without fetal heart beat as documented by ultrasound or surgery

Concerning timing, a pregnancy loss occurring before ongoing pregnancy (i.e. during 1st trimester) will be defined as an early pregnancy loss, while a pregnancy loss occurring after ongoing pregnancy (i.e. during 2nd or 3rd trimester) during the post-trial follow-up will be defined as a late pregnancy loss.

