## **9.9 Post-trial Activities**

A separate SAP will be prepared to cover the post-trial information.

The number and percentage of subjects with live birth will be presented by treatment group. Subjects with no information on live birth will be defaulted to a negative response.

Neonatal health, including minor/major congenital anomalies, at birth and at 4 weeks after birth will be presented by treatment group.

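### Two low-severity slips in SAP safety definitions: the markedly abnormal high-pulse criterion is practically unreachable, and an unknown birth outcome, read literally, counts as a late pregnancy loss

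*SAP*

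**What the plan says.** **Pulse.** SAP Appendix 1 Table 4 sets two-part criteria for markedly abnormal vital signs: an absolute limit and a change from baseline. For high pulse the limit is above 130 and the change is a rise of at least 150. The reference range in the same table flags pulse below 50 as low and above 100 as high. SAP 10.11.4 uses the table in three ways:

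- shift tables based on the reference range;
- a summary of markedly abnormal values, for systolic and diastolic pressure only;
- a listing in which low, high and markedly abnormal values are flagged.

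The introduction to Appendix 1 describes the criteria as project standards that were also used in ESTHER.

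**Late loss.** SAP 10.12, Late Pregnancy Loss, states: "A late pregnancy loss is defined as an ongoing pregnancy not followed by live birth". The incidence is tabulated for the safety analysis set, with all subjects who had an ongoing pregnancy as denominator. The same section adds: "The reason for no live birth (still birth, miscarriage, elective termination) will be tabulated at the fetus/neonate level". Under Live Birth, SAP 10.12 states: "Subjects with no information on a live birth will be regarded as not having live birth". Protocol 9.9 has the same default: "Subjects with no information on live birth will be defaulted to a negative response".

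**The concern.** A rise of 150 is ten times the fall of 15 used for low pulse, and the table is otherwise symmetric. A criterion that no plausible value meets does no work: an empty flag column would look like reassurance when it only reflects the threshold.

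For late loss, the trouble comes from reusing a default outside its purpose. Treating missing information as no live birth is a common cautious rule for a success rate. Carried into a loss count, it turns missing follow-up into adverse pregnancy outcomes. A programmer who derives late loss as ongoing pregnancy present and live birth absent would follow the SAP to the letter and produce exactly that. A woman counted only through the default would have none of the three listed reasons.

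**Working it through.** The plan gives no calculated figure for either definition, so there is none to reproduce. The sample size serves only for scale.

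**1. Pulse criterion**

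Changes required in Appendix 1 Table 4:

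| Variable | Fall (low) | Rise (high) |
|---|---|---|
| Systolic pressure | ≥20 | ≥20 |
| Diastolic pressure | ≥15 | ≥15 |
| Pulse | ≥15 | ≥150 |

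With baseline b, the flag needs a pulse above 130 and at least b + 150. Since b + 150 exceeds 130 for every baseline, the 130 limit never operates.

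- b = 50: 50 + 150 = 200.
- b = 100: 100 + 150 = 250.

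For illustration only, suppose the rise matched the low side (15). The 130 limit would then operate for every baseline up to 130 − 15 = 115, and baselines of 50-100 would be flagged from 131. The documents do not say which value was intended.

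**2. Late loss: the passages side by side**

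- The Live Birth text assigns a status: no information means no live birth.
- The Late Pregnancy Loss text uses that status: ongoing pregnancy without live birth means late loss.
- The denominator removes nobody with unknown outcome.
- No sentence confines the default to the live birth rate.

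Other passages describe an actual event. Protocol 8.3.6 speaks of "a pregnancy loss occurring after ongoing pregnancy". SAP 10.9 says: "Early pregnancy loss is defined as pregnancy loss occurring before ongoing pregnancy". The listed reasons (still birth, miscarriage, elective termination) are all documented events, with no category for unknown.

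**3. Size per unknown outcome**

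Inputs: 1,000 randomised and a 32.2% ongoing pregnancy rate (Protocol 9.1, SAP 3.2); a maximum of 1,144 at a 50% rate (Protocol 9.10, SAP 3.2). I assume equal arms and that all randomised women are exposed.

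- Planned size: 500 × 0.322 = 161 ongoing pregnancies per arm. One unknown adds 1/161 = 0.6 points.
- Maximum size: 572 × 0.50 = 286 per arm. One unknown adds 1/286 = 0.35 points.

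For k unknown outcomes in an arm (k is assumed; the documents give no number), the addition is k/161 or k/286:

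| k | Planned size | Maximum size |
|---|---|---|
| 0 | 0 | 0 |
| 1 | 0.6 points | 0.35 points |
| 2 | 1.2 points | 0.7 points |
| 5 | 3.1 points | 1.7 points |

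The table is also split by age stratum and country, where denominators are smaller and one case weighs more.

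**The case against.** The carry-over into late loss is implied and never stated. The default sits under Live Birth, a rate analysed in the FAS and PP sets. Late Pregnancy Loss has its own definition, analysis set and denominator, and does not refer to the default. Protocol 8.3.6 describes a real loss, and SAP section 12 announces no change on this point. All of this stands, and it makes documented loss the more coherent reading. It does not remove the literal one, because the sentence that defines the table turns on the absence of live birth.

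Follow-up is also meant to be complete. Protocol 6.10 says: "All subjects with an ongoing pregnancy will be followed till delivery to gather information on live birth rate". Protocol 14.7 gives subjects a reminder checklist, and SAP 10.12 commits to accounting for every viable fetus and to listing the follow-up data. Unknown outcomes may therefore be few or none. The table shells are in another document, and Protocol 9.9 says: "A separate SAP will be prepared to cover the post-trial information". Either may already contain a row for unknown outcome.

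One could defend counting unknowns as losses as the cautious choice for safety. SAP 10.1 does impute the worst case for adverse events, but only for causality, intensity and seriousness of an event already reported. It does not create events. Conversely, keeping unknowns in the denominator without counting them as losses can understate the rate slightly. A visible row for unknown outcome lets the reader judge that.

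On pulse, the digit could be an artefact of the published copy, and its only effect is a listing flag. Both are fair, and they are why this is a query to be checked.

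A reader might infer more: that the plan deliberately treats women lost to follow-up as losses, that the late-loss comparison between arms is biased, or that high pulse values will go unseen. The documents support none of these. No test of late loss is planned, nothing is said about how many outcomes will be unknown in either arm, and the flag above 100 and the shift table still show raised pulse values.

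**Conclusion.** Both points hold at low severity. The high-pulse criterion is defective as printed: its absolute limit is redundant, and a baseline within the reference range would need a pulse of 200-250. That follows from the table alone. The consequence is confined to the markedly abnormal flag in the vital signs listing; the blood pressure summary does not use it.

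The late-loss wording allows two readings, and the literal one counts unknown outcomes as losses in a descriptive table. Its effect is zero with no unknown outcomes and about 0.6 points per unknown in an arm at the planned size, assuming 161 ongoing pregnancies per arm. No overall distortion can be estimated, because the documents give neither the number of unknown outcomes nor an expected late-loss rate. The primary endpoint, the sample size and all planned tests are unaffected. The no-information default is reasonable for the live birth rate itself.

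**What to change.** 1. **Appendix 1 Table 4.** Check the high-pulse increment against the signed SAP and the project standard named in the introduction to Appendix 1, then correct it to the value in that standard.
2. **SAP 10.12, Late Pregnancy Loss.** State that a late loss is counted only when a loss is documented, naming which of the listed reasons qualify; that the no-information default applies to the live birth rate only; and that ongoing pregnancies with unknown birth outcome appear in their own row, with all ongoing pregnancies as denominator. This also carries out the section's commitment to account for all viable fetuses. Make the table shells and any separate post-trial SAP agree.

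The cost is one number, one clarifying sentence and one table row. No new data are needed and no planned analysis changes. It should be done before the tables are programmed.

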### **Neonatal Health at Birth and at 4 Weeks after Birth**

Neonatal health at birth and at 4 weeks after birth, including minor/major congenital anomalies, will be summaries for all live-born neonates. Summaries includes delivery details, gestational age, gender, birth weight and birth length. Admission to neonatal intensive care unit and/or neonatal care unit will be summaries at birth and at 4 weeks after birth, including the reasons for admissions. The Apgar score at 1, 5 and 10 minutes after birth will be summarised. Neonates will be grouped according to the Apgar score for each assessment time as: 0-3, 4-6, 7-10 and the corresponding frequencies tabulated. These data will be summarised by the treatment group and age stratum, and by treatment group and pregnancy type (singletons, twins), for the safety analysis set. Separate tables will be produced by country.

### **Incidence of Serious Adverse Events**

All serious adverse events will be coded using MedDRA. In addition, congenital anomalies on the fetus/neonates will be coded using ICD-10 and these events will be classified as minor or major in accordance with the EMA guideline.

All serious adverse events will be listed.

Summary tables will be produced for the following:

- Maternal serious adverse events by SOC and PT
- Neonatal serious adverse events by SOC and PT
- Congenital anomalies on the fetus/neonates by ICD-10
- Congenital anomalies on the fetus/neonates classification as major by ICD-10
- Congenital anomalies on the fetus/neonates classification as minor by ICD-10

## 11 Interim Analyses

No interim analysis intended to compare treatments with respect to efficacy or safety is planned.

A sample size re-assessment is planned and will be done without breaking the blind and without inflating the type 1 error of the trial, in line with the current regulatory guidelines (see Section 3.2).

## 12 Changes Compared to the Analyses Described in the Trial Protocol

There are no changes to the primary analysis planned in the protocol for the primary endpoint. The sensitivity analyses planned on subgroups of subjects (subjects with oocytes retrieved and subjects with transfer) have been excluded since these analyses do not adhere to the randomisation principle. Descriptive statistics will be used to present the results in the subgroups.

For the secondary endpoints, details and context of the analyses described in the protocol have been clarified and some additional analyses have been included to make the result description more complete. The proposed analyses for ordinal data have been excluded since there are no ordinal endpoints. For example a grouping based on increasing number of oocytes retrieved is ordinal, however, the corresponding ovarian response (low response, moderate response, target response, hyperresponse, severe hyperresponse) is not ordinal. The treatment comparisons will be carried out as planned based on the ungrouped data.

## **14 Tables, Listings and Figures**

Shells for tables, figures and listings will be presented in a separate document.

## Appendix 1 Markedly Abnormal Laboratory Safety Values and Vital Signs

The markedly abnormal laboratory safety values and vital signs presented in this Appendix are FE 999049 project standards. The same criteria were applied to the data captured in the ESTHER trial.

**Table 1: Markedly Abnormal Criteria for Haematology**

Variable	Units	Markedly abnormal criteria	
		Low	High
Haemoglobin	g/L	≤ 115	Not applicable
Haematocrit	Ratio	≤ 0.37	≥ 0.56
Total WBC	10  /L	≤ 2.8	≥ 16.0
Eosinophils	%	Not applicable	≥ 10
Neutrophils	%	≤ 15	≥ 90
Lymphocytes	%	≤ 10	≥ 80
Monocytes	%	Not applicable	≥ 20
Basophils	%	Not applicable	≥ 5
Bands	%	Not applicable	≥ 20
Platelets	10  /L	≤ 75	≥ 700
Total RBC	10  /L	≤ 3.5	Not applicable

RBC: Red blood cells, WBC: White blood cells.

**Table 2: Markedly Abnormal Criteria for Clinical Chemistry**

Variable	Units	Markedly abnormal criteria	
		Low	High
Albumin	g/L	< 20	Not applicable
ALT	IU/L	Not applicable	> 3xULN
Alkaline phosphatase	IU/L	Not applicable	> 3xULN
AST	IU/L	Not applicable	> 3xULN
Bicarbonate	mmol/L	< 15.1	> 34.9
Bilirubin direct	umol/L	Not applicable	> 2xULN
Bilirubin total	umol/L	Not applicable	> 2xULN
Blood urea nitrogen	mmol/L	Not applicable	> 12.5
Calcium	mmol/L	< 1.75	> 2.74
Chloride	mmol/L	Not applicable	Not applicable
Cholesterol (30-40Y)	mmol/L	Not applicable	> 10.34
Creatinine	umol/L	Not applicable	> 3xULN
GGT	IU/L	Not applicable	> 3xULN
Glucose	mmol/L	< 2.5	> 16.7
LDH	IU/L	Not applicable	> 3xULN
Phosphate	mmol/L	< 0.6	Not applicable
Potassium	mmol/L	< 3.0	> 5.8
Sodium	mmol/L	< 125	> 155
Total protein	g/L	< 20	> 90
Uric acid	umol/L	Not applicable	> 595

ALT: Alanine Aminotransferase, AST: Aspartate Aminotransferase, GGT: Gamma Glutamyl Transferase,  
 LDH: Lactate Dehydrogenase.

**Table 3: Markedly Abnormal Criteria for Endocrine Parameters**

Variable	Unit	Markedly abnormal criteria (high)
LH	IU/L	> 10
Progesterone	nmol/L	> 3.18
LH and progesterone	Not applicable	LH > 10 IU/L and progesterone > 3.18 nmol/L on the same day

LH: Luteinising Hormone.

**Table 4: Reference Ranges and Markedly Abnormal Criteria for Vital Signs**

Variable	Reference range		Markedly abnormal criteria	
	Low	High	Low	High
Systolic blood pressure (mmHg)	<90	>140	< 80 and decrease of $\geq 20$ from baseline	> 155 and increase of $\geq 20$ from baseline
Diastolic blood pressure (mmHg)	<60	>90	< 50 and decrease of $\geq 15$ from baseline	> 100 and increase of $\geq 15$ from baseline
Pulse rate (bmp)	<50	>100	< 45 and decrease of $\geq 15$ from baseline	> 130 and increase of $\geq 150$ from baseline
